8. ADVERSE EVENTS: LIST AND REPORTING REQUIREMENTS

8.1 Adverse events

See Investigator's brochure for BMS-986253 and **Section 11** for details.

8.2 Definitions

Adverse Event:

An Adverse Event (AE) is defined as any new untoward medical occurrence or worsening of a preexisting medical condition in a clinical investigation participant administered study drug and that does not necessarily have a causal relationship with this treatment. An AE can therefore be any unfavorable and unintended sign (such as an abnormal laboratory finding), symptom, or disease temporally associated with the use of investigational product, whether or not considered related to the investigational product.

The causal relationship to study drug is determined by a physician and should be used to assess all adverse events (AE). The causal relationship can be one of the following:

Related: There is a reasonable causal relationship between study drug administration and the AE.

Not related: There is not a reasonable causal relationship between study drug administration and the AE.

The term "reasonable causal relationship" means there is evidence to suggest a causal relationship.

Adverse events can be spontaneously reported or elicited during open-ended questioning, examination, or evaluation of a subject. (In order to prevent reporting bias, subjects should not be questioned regarding the specific occurrence of one or more AEs.)

Serious Adverse Event:

A **Serious Adverse Event (SAE)** is any untoward medical occurrence that at any dose:

- results in death
- is life-threatening (defined as an event in which the participant was at risk of death at the time of the event; it does not refer to an event which hypothetically might have caused death if it were more severe)
- requires inpatient hospitalization or causes prolongation of existing hospitalization (see **NOTE** below)
- results in persistent or significant disability/incapacity
- is a congenital anomaly/birth defect
- is an important medical event (defined as a medical event(s) that may not be immediately life-threatening or result in death or hospitalization but, based upon appropriate medical and scientific judgment, may jeopardize the subject or may require intervention [eg, medical, surgical] to prevent one of the other serious outcomes listed in the definition above.) Examples of such events include, but are not limited to, intensive treatment in an emergency room or at home for allergic bronchospasm; blood dyscrasias or convulsions that do not result in hospitalization.)
- Suspected transmission of an infectious agent (eg, pathogenic or nonpathogenic) via the study drug is an SAE.

Although pregnancy, overdose, potential drug-induced liver injury (DILI), and cancer are not always serious by regulatory definition, these events must be handled as SAEs.

Any component of a study endpoint that is considered related to study therapy should be reported as an SAE (eg, death is an endpoint, if death occurred due to anaphylaxis, anaphylaxis must be reported).

The following hospitalizations are not considered SAEs in BMS clinical studies:

- a visit to the emergency room or other hospital department < 24 hours, that does not result in admission (unless considered an important medical or life-threatening event)
- elective surgery, planned prior to signing consent
- admissions as per protocol for a planned medical/surgical procedure
- routine health assessment requiring admission for baseline/trending of health status (eg, routine colonoscopy)
- Medical/surgical admission other than to remedy ill health and planned prior to entry into the study. Appropriate documentation is required in these cases.
- Admission encountered for another life circumstance that carries no bearing on health status and requires no medical/surgical intervention (eg, lack of housing, economic inadequacy, caregiver respite, family circumstances, administrative reason).
- Admission for administration of anticancer therapy in the absence of any other SAEs (applies to oncology protocols)

Non-serious Adverse Event:

- Non-serious Adverse Events (AE) are to be provided to BMS in aggregate via interim or final study reports as specified in the agreement or, if a regulatory requirement [eg, IND US trial] as part of an annual reporting requirement.

A ***non-serious adverse event*** is an AE not classified as serious.

Non-serious Adverse Event Collection and Reporting

The collection of serious and non-serious AE information should begin at initiation of study drug. All serious non-serious adverse events (not only those deemed to be treatment-related) should be collected continuously during the treatment period and for a minimum of 100 days following the last dose of study treatment.

Non-serious AEs should be followed to resolution or stabilization, or reported as SAEs if they become serious. Follow-up is also required for non-serious AEs that cause interruption or discontinuation of study drug and for those present at the end of study treatment as appropriate.

Laboratory Test Abnormalities

All laboratory test results captured as part of the study should be recorded following institutional procedures. Test results that constitute SAEs should be documented and reported to BMS as such.

The following laboratory abnormalities should be documented and reported appropriately:

- any laboratory test result that is clinically significant or meets the definition of an SAE
- any laboratory abnormality that required the participant to have study drug discontinued or interrupted
- any laboratory abnormality that required the subject to receive specific corrective therapy.

It is expected that wherever possible, the clinical rather than laboratory term would be used by the reporting investigator (eg, anemia versus low hemoglobin value).

Potential Drug Induced Liver Injury (DILI)

All occurrences of potential DILIs, meeting the defined criteria, must be reported as SAEs. Potential drug induced liver injury is defined as:

- 1) AT (ALT or AST) elevation > 3 times upper limit of normal (ULN)
AND
- 2) Total bilirubin > 2 times ULN, without initial findings of cholestasis (elevated serum alkaline phosphatase)
AND
- 3) No other immediately apparent possible causes of AT elevation and hyperbilirubinemia, including, but not limited to, viral hepatitis, pre-existing chronic or acute liver disease, or the administration of other drug(s) known to be hepatotoxic.

Pregnancy

DEFINITIONS

Woman of Childbearing Potential (WOCBP)

A woman is considered fertile following menarche and until becoming post-menopausal unless permanently sterile. Permanent sterilization methods include hysterectomy, bilateral salpingectomy, and bilateral oophorectomy.

WOMEN IN THE FOLLOWING CATEGORIES ARE NOT CONSIDERED WOCBP

- Premenarchal
- Premenopausal female with 1 of the following:
 - Documented hysterectomy
 - Documented bilateral salpingectomy
 - Documented bilateral oophorectomy

Note: Documentation can come from the site personnel's review of the participant's medical records, medical examination, or medical history interview.

- Postmenopausal female
 - A postmenopausal state is defined as 12 months of amenorrhea in a woman over age 45 years in the absence of other biological or physiological causes. In addition, females under the age of 55 years must have a serum follicle stimulating hormone, (FSH) level

> 40 mIU/mL to confirm menopause.

Note: Women treated with hormone replacement therapy (HRT) are likely to have artificially suppressed FSH levels and may require a washout period in order to obtain a physiologic FSH level. The duration of the washout period is a function of the type of HRT used. The duration of the washout periods indicated below are suggested guidelines, and the investigators should use their judgement in checking serum FSH levels.

- 1 week minimum for vaginal hormonal products (rings, creams, gels)
- 4 week minimum for transdermal products
- 8 week minimum for oral products

Other parenteral products may require washout periods as long as 6 months. If the serum FSH level is > 40 mIU/ml at any time during the washout period, the woman can be considered postmenopausal.

CONTRACEPTION GUIDANCE FOR FEMALE PARTICIPANTS OF CHILD BEARING POTENTIAL

One of the highly effective methods of contraception listed below is required during study duration

and until the end of relevant systemic exposure, which is defined as 105 days after completion of study treatment for monotherapy treatment and 155 days after completion of combination therapy treatment.

Local laws and regulations may require use of alternative and/or additional contraception methods.

Highly Effective Contraceptive Methods That Are User Dependent
Failure rate of <1% per year when used consistently and correctly.^a

• Combined (estrogen- and progestogen-containing) hormonal contraception associated with inhibition of ovulation^b
– oral– intravaginal– transdermal• Progestogen-only hormonal contraception associated with inhibition of ovulation^b
– oral– injectable
Highly Effective Methods That Are User Independent

• Implantable progestogen-only hormonal contraception associated with inhibition of ovulation^b• Intrauterine device^c• Intrauterine hormone-releasing system^c• Bilateral tubal occlusion

- Vasectomized partner

A vasectomized partner is a highly effective contraception method provided that the partner is the sole male sexual partner of the WOCBP and the absence of sperm has been confirmed. If not, an additional highly effective method of contraception should be used.

- Sexual abstinence

Sexual abstinence is considered a highly effective method only if defined as refraining from heterosexual intercourse during the entire period of risk associated with the study drug. The reliability of sexual abstinence needs to be evaluated in relation to the duration of the study and the preferred and usual lifestyle of the participant.

- It is not necessary to use any other method of contraception when complete abstinence is elected.
- WOCBP participants who choose complete abstinence must continue to have pregnancy tests.
- Acceptable alternate methods of highly effective contraception must be discussed in the event that the WOCBP participants chooses to forego complete abstinence.

NOTES:

^a Typical use failure rates may differ from those when used consistently and correctly. Use should be consistent with local regulations regarding the use of contraceptive methods for participants participating in clinical studies.

^b Hormonal contraception may be susceptible to interaction with the study drug, which may reduce the efficacy of the contraceptive method. Hormonal contraception is permissible only when there is sufficient evidence that the IMP and other study medications will not alter hormonal exposures such that contraception would be ineffective or result in increased exposures that could be potentially hazardous. In this case, alternative methods of contraception should be utilized.

^c Intrauterine devices and intrauterine hormone releasing systems are acceptable methods of contraception in the absence of definitive drug interaction studies when hormone exposures from intrauterine devices do not alter contraception effectiveness

Less Than Highly Effective Contraceptive Methods That Are User Dependent

Failure rate of >1% per year when used consistently and correctly.

- Male or female condom with or without spermicide. Male and female condoms cannot be used simultaneously
- Diaphragm with spermicide
- Cervical cap with spermicide
- Vaginal Sponge with spermicide
- Progestogen-only oral hormonal contraception, where inhibition of ovulation is not the primary mechanism of action

Unacceptable Methods of Contraception

- Periodic abstinence (calendar, symptothermal, post-ovulation methods)
- Withdrawal (coitus interruptus).
- Spermicide only
- Lactation amenorrhea method
-

Any pregnancy that occurs in a female or female partner of a male study participant should be reported to BMS. All pregnancy cases should be reported, within 5 months after the last exposure to BMS-986253. Information on this pregnancy will be collected on the Pregnancy Surveillance Form. In order for Sponsor or designee to collect any pregnancy surveillance information from the female partner, the female partner must sign an informed consent form for disclosure of this information.

Contraception Guidance for Male Participants with Partner(s) of Child Bearing Potential

Male participants with female partners of childbearing potential are eligible to participate if they agree to the following during the treatment and until the end of relevant systemic exposure.

- Inform any and all partner(s) of their participation in a clinical drug study and the need to comply with contraception instructions as directed by the investigator.
- Male participants are required to use a condom for study duration and until the end of relevant systemic exposure defined as 7 months Relevant Exposure after the end of treatment in the male participant.
- Female partners of males participating in the study to consider use of effective methods of contraception until the end of relevant systemic exposure, defined as 7 months Relevant Exposure after the end of treatment in the male participant.
- Male participants with a pregnant or breastfeeding partner must agree to remain abstinent from penile vaginal intercourse or use a male condom during each episode of penile penetration during the treatment and until 7 months Relevant Exposure after the end of treatment.
- Refrain from donating sperm for the duration of the study treatment and for 7 months after the end of treatment.

Overdose

An overdose is defined as the accidental or intentional administration of any dose of a product that is considered both excessive and medically important. All occurrences of overdose must be reported as an SAE.

Other Safety Considerations

Any significant worsening noted during interim or final physical examinations, electrocardiograms, X-rays, and any other potential safety assessments, whether or not these

procedures are required by the protocol, should also be recorded as a non-serious or serious AE, as appropriate, and reported accordingly.

Adverse Events of Special Interest:

An AESI is an event of scientific and medical interest or concern to the Sponsor's product or program, for which ongoing monitoring and rapid communication to the Sponsor could be appropriate. It may be a serious or non-serious AE, which may require further investigation in order to characterize and understand it.

AESI will include the following:

- Grade 3 or greater infusion reaction including CRS; and,
- Immune related AE of Grade 3 or greater suggestive of an autoimmune process, including, but not limited to, glomerulonephritis.

Important medical events are those that may not be immediately life threatening, but are clearly of major clinical significance. They may jeopardize the subject, and may require intervention to prevent one of the other serious outcomes noted above. For example, drug overdose or abuse, a seizure that did not result in in-patient hospitalization or intensive treatment of bronchospasm in an emergency department would typically be considered serious.

All adverse events that do not meet any of the criteria for serious events should be regarded as non-serious adverse events.

Unanticipated Problem:

An unanticipated problem is any incident, experience or outcome involving risks to subjects or others in any human subjects research that meets all of the following criteria:

- Unexpected (in terms of nature, severity or frequency) given (a) the research procedures that are described in the IRB-approval protocol and informed consent document, and (b) the characteristics of the subject population being studied;
- Related or possibly related to participation in such research (e.g., there is a reasonable possibility that the incident, experience or outcome may have been caused by the procedures involved in such research); and
- Suggests that the research places subjects or others at a greater risk of harm (including physical, psychological, economic or social harm) than was previously known or recognized.

Adverse Event Reporting Period

The study period during which adverse events must be reported is normally defined as the period from the initiation of any study procedures (e.g., after the first dose of study treatment) to the end of the study treatment (e.g., last dose of study treatment) and/or follow-up. For this study, the study treatment follow-up is defined as 100 days following the last administration of study treatment.

Baseline/Preexisting Condition

A baseline/preexisting condition is one that is present at the start of the study. A preexisting condition should be recorded as an adverse event if the frequency, intensity, or if the character of the condition worsens during the study period.

General Physical Examination Findings

At screening, any clinically significant abnormality should be recorded as a preexisting condition. At the end of the study, any new clinically significant findings/abnormalities that meet the definition of an adverse event must also be recorded and documented as an adverse event.

Post-study Adverse Event

All unresolved adverse events should be followed by the investigator until the events are resolved, the subject is lost to follow-up, or the adverse event is otherwise explained. At the last scheduled visit, the investigator should instruct each subject to report any subsequent event(s) that the subject, or the subject's personal physician, believes might reasonably be related to participation in this study.

Abnormal Laboratory Values

A clinical laboratory abnormality should be documented as an adverse event if any one of the following conditions is met:

- The laboratory abnormality is not otherwise refuted by a repeat test to confirm the abnormality
- The abnormality suggests a disease and/or organ toxicity
- The abnormality is of a degree that requires active management (e.g., change of dose, discontinuation of the drug, more frequent follow-up assessments, further diagnostic investigation, etc.).

Hospitalization, Prolonged Hospitalization or Surgery

Any adverse event that results in hospitalization or prolonged hospitalization should be documented and reported as a serious adverse event unless specifically instructed otherwise in this protocol. Any condition responsible for surgery should be documented as an adverse event if the condition meets the criteria for an adverse event.

Neither the condition, hospitalization, prolonged hospitalization, nor surgery are reported as an adverse event in the following circumstances:

- Hospitalization for >24 hours or prolonged hospitalization for diagnostic or elective surgical procedures for a preexisting condition. Surgery should **not** be reported as an outcome of an adverse event if the purpose of the surgery was elective or diagnostic and the outcome was uneventful.
- Hospitalization or prolonged hospitalization required to allow efficacy measurement for the study.

- Hospitalization or prolonged hospitalization for therapy of the target disease of the study, unless it is a worsening or increase in frequency of hospital admissions as judged by the clinical investigator.

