8.4.4 Reporting to Drug Manufacturers by Sponsor-Investigator

The Sponsor-Investigator will report to investigational agent manufacturers any serious adverse events that meet the reporting criteria to the Institutional Review Board as described in section 10.4 and/or to the FDA as described in section 10.4 within 3 days of becoming aware of it, so that these reports can be evaluated and included in the Investigator's Brochure and for IND safety submissions per regulations. Reporting will occur by sending the reporting form along with any additional documentation sent to the regulatory authorities.

At the time of IRB renewal or at the request of the manufacturer, the Sponsor- Investigator will submit a summary of all Serious Adverse Events that have occurred inclusive of all sites to manufacturer.

All Serious Adverse Events (SAEs) that occur following the subject's treatment start date to participate in the study through 100 days of discontinuation of dosing must be reported to BMS Worldwide Safety and to Ferring Safety, whether related or not related to study drug. If applicable, SAEs must be collected that relate to any later protocol-specified procedure (eg, a follow-up skin biopsy).

Following the subject's treatment start date, all SAEs, whether related or not related to study drug, are collected, including those thought to be associated with protocol-specified procedures. The investigator should report any SAE occurring after these aforementioned time periods, which is believed to be related to study drug or protocol-specified procedure.

- An SAE report should be completed for any event where doubt exists regarding its seriousness;
- If the investigator believes that an SAE is not related to study drug, but is potentially related to the conditions of the study (such as withdrawal of previous therapy or a complication of a study procedure), the relationship should be specified in the narrative section of the SAE Report Form.

An appropriate SAE form (e.g. ex-US = CIOMS form or USA = Medwatch form) or equivalent (HICCC DSMC SAE Form) should be used to report SAEs to BMS. Note: Please include the BMS Protocol number on the SAE form or on the cover sheet with the SAE form transmission.

- The CIOMS form is available at: <http://www.cioms.ch/index.php/cioms-form-i>
- The MedWatch form is available at: [MedWatch 3500 Form](#)
-
- **SAE reporting to BMS:**

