- review of medication list daily
- review of toxicity/adverse events daily
- vital signs (pre- and post-infusion of BMS-986253) and three times per day including temperature, heart rate, blood pressure, respiratory rate, oxygen saturation and FIO₂ and SpO₂/FIO₂ if on supplementation oxygen.
- physical exam daily
- hematological laboratories (hemoglobin, hematocrit, white blood cell count with differential [including absolute eosinophil count], platelets) daily
- coagulation profile (INR, aPTT) as clinically indicated.
- serum chemistry profile (sodium, potassium, chloride, bicarbonate, urea, creatinine, glucose, calcium, albumin, total protein, bilirubin, ALT, AST, alkaline phosphatase) daily
- CRP, D-Dimer, LDH, sIL-6 level every other day
- Neutrophil-to-lymphocyte ratio (NLR), absolute lymphocyte count daily
- NEWS2 score daily
- 7-point ordinal score daily
- CT or CXR of the chest weekly (+/- 2 days) (optional)
- Sera for biomarker and PK analysis day 8, 15, 22, 29, and EOT (+/- 2 days). Where possible, the Day 15 and 29 PK samples should be collected just prior to dosing (optional). For patients ready for discharge prior to day 8, a serum sample should be collected, when feasible, prior to discharge.
- Patients randomized to anti-IL-8 therapy will receive BMS-986253 every 2 weeks (+/- 2 days) x 1-3 doses, with 2nd dose given if patient still hospitalized and then 3rd dose optional if patient still hospitalized with severe COVID-19. Patients randomized to control will receive standard of care.

10.3 Follow-Up After Discharge:

Following completion of therapy, patient will have follow up by phone every 30 days for the first 100 days following the last dose of therapy. Patients will then have follow up by phone every 90 days (+/- 30 days) for up to 1 year. In addition, patients will be assessed 28 days (+/- 2 days) following start of treatment whether they are discharged or in the hospital. These assessments will include:

- review of medication list
- review of toxicity/adverse events (for up to 100 days following last dose of treatment)
- Evaluation of Katz basic ADLs and Lawton IADLs (Appendix C and D)

- assessment for survival

Patients withdrawing from the study early because of adverse events should be followed until the adverse event has either resolved or stabilized. Reasons for premature withdrawal should be determined and documented.

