13.6 Safety Analysis

All subjects receiving at least one dose of the study drug will be evaluated for safety by monitoring symptoms, physical examinations, and laboratory tests. Adverse events will be classified and graded according to the NCI Common Toxicity Criteria version 5.0 (see Appendix B). The absolute number and frequency of each adverse event will be reported, and subdivided according to toxicity grade. A description of adverse events by treatment arm will also be reported. A particular adverse event occurring more than once in the same subject will be counted only once and at its worse grade. At the end of study, the cumulative incidences of these events will be compared between the two treatment groups using Fisher's exact test.

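### Adverse-event collection is anchored to study-drug doses, so controls have no defined collection window and the planned between-arm comparison can be biased

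*Combined protocol and SAP*

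**What the plan says.** - **Start.** Section 8.2: "The collection of serious and non-serious AE information should begin at initiation of study drug".
- **End.** The same section continues collection "for a minimum of 100 days following the last dose of study treatment", and its reporting-period paragraph adds that "the study treatment follow-up is defined as 100 days following the last administration of study treatment". Section 4.1, note h of the study calendar (Section 10) and Section 10.3 use the same end anchor. Sections 7.7 and 10.3 set the calls the same way: "patient will have follow up by phone every 30 days for the first 100 days following the last dose of therapy".
- **Definition.** Section 8.2 defines an adverse event as one arising "in a clinical investigation participant administered study drug".
- **Dosing.** Section 7.1 schedules days 1, 15 and 29. The second dose is given only if the patient is still hospitalized. The third is optional and also requires severe respiratory symptoms.
- **Comparison.** Section 2 makes safety relative to controls a secondary objective. Section 13.2 plans chi-squared or Fisher tests. Section 13.6 says that "the cumulative incidences of these events will be compared between the two treatment groups using Fisher's exact test".
- **Safety set.** Sections 13.5.2 and 13.6 confine it to patients who had at least one dose of study drug.
- **Text not limited to one arm.** The calendar and Section 10.2 require daily toxicity review in hospital. Section 10.3 assesses patients 28 days after start of treatment, including an adverse-event review. Section 8.3 requires questioning about adverse events at every contact. Section 13.1 has discharged patients called on day 29 and then monthly for up to a year.

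**The concern.** A control has no first dose and no last dose. The stated rules therefore neither open nor close adverse-event collection for that patient, and staff would have to improvise. In the drug arm the window lengthens with each dose, and later doses depend on continued hospitalization, so the sicker treated patients are observed longest.

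A Fisher test on the proportion of patients with an event takes no account of time observed. If controls are in practice covered for less time, the drug looks more toxic than it is. The control rate is also the trial's only internal way to separate drug harm from complications of COVID-19. Events that were never collected cannot be recovered at analysis.

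**Working it through.** The plan states no control window and no background adverse-event rate, so there is no figure of its own to reproduce.

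**1. Treated window.** With the last dose on day d (Section 7.1), collection runs at least to day d + 100, a length of (d − 1) + 100 days from day 1.

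| Doses | Last dose | Ends no earlier than | Length | Relative to one dose |
|---|---|---|---|---|
| 1 | day 1 | day 101 | 100 days | 1.00 |
| 2 | day 15 | day 115 | 114 days | 1.14 |
| 3 | day 29 | day 129 | 128 days | 1.28 |

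Note g of the calendar allows ±2 days on dosing. A third dose on day 31 gives 31 + 100 = day 131. If both intervals run two days late, the dose falls on day 33 and the end on day 133.

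**2. Control window.** Two parts of the plan clearly reach controls: daily in-hospital review, and the assessment at about day 28/29. Sections 8.3 and 13.1 imply later questioning, but neither gives an end date for adverse events.

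**3. Effect on Fisher's test.** Inputs from the plan: 92 and 46 patients (Section 13.1). Assumptions: two-sided 5% test, all randomized patients analysed, no drug effect, controls covered to day 28, treated patients to day 100. The result is the exact rejection probability over two independent binomials.

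(a) Constant hazard: λ = −ln(1 − p28)/28 and p(t) = 1 − exp(−λt), where p28 is the assumed day-28 incidence.

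| p28 (controls) | p100 (treated) | Rejection, 100 vs 28 days | Rejection, both 100 days |
|---|---|---|---|
| 5% | 16.7% | 0.465 | 0.038 |
| 10% | 31.4% | 0.822 | 0.039 |
| 20% | 54.9% | 0.983 | 0.046 |
| 30% | 72.0% | 0.998 | 0.039 |

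(b) Front-loaded risk: treated incidence p100, control incidence f × p100, where f is the share of events occurring by day 28.

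| p100 | f = 60% | f = 80% | f = 90% |
|---|---|---|---|
| 10% | 0.063 | 0.035 | 0.032 |
| 20% | 0.178 | 0.066 | 0.044 |
| 30% | 0.301 | 0.095 | 0.052 |
| 40% | 0.422 | 0.126 | 0.061 |

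**4. Dose-dependent lengthening alone.** Same constant hazards, with controls at 100 days. If every treated patient had 128 days (an upper bound), rejection is 0.068 to 0.171. If every treated patient had 114 days, it is 0.045 to 0.076. This is the smaller component.

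**5. Safety set.** Read literally, Section 13.5.2 admits up to 92 treated patients and no undosed controls. Aligning the windows would not by itself restore a comparison.

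**The case against.** The strongest reply is that controls are in fact followed for adverse events. In Section 10.2 only the dosing item is split by arm. The day-28 assessment applies whether or not the patient has been discharged. Section 8.3 asks about adverse events at every contact, and Section 13.1 has calls for a year. Section 8.2 also mentions a start at any study procedure, although its example is the first dose.

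Much of this stands, and it rules out several stronger readings that a reader might infer:

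- *Controls have no adverse-event collection.* Not supported. They have collection, but no stated start or end. Nor can one assume that control coverage stops at discharge, because the day 28/29 assessment contradicts that.
- *The safety comparison is invalid.* Not shown. If about 90% of events occur by day 28, the test stays close to nominal, and for an acute illness front-loading is plausible.
- *Days 91 to 100 after the last dose are uncovered.* Not supported. Calendar note f allows ±1 week, so a day-90 call can fall on day 97. Section 13.1 has monthly calls beyond that, and a call can ask about the preceding interval.
- *The manufacturer rule in Section 8.4.4 is part of the defect.* That rule, under which serious events "through 100 days of discontinuation of dosing must be reported to BMS Worldwide Safety", governs reporting on a product. A drug anchor is unremarkable there.

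The reply does not supply a control window. Section 8.3 records events during the study period, which Section 8.2 defines by dosing. Section 10.3 limits adverse-event review to 100 days after the last dose. The calls in Section 13.1 are described as checks on status.

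**Conclusion.** The concern holds as a gap in definition that affects data capture. Controls have no defined adverse-event window, while the treated window has a minimum of 100 to 128 days that lengthens with continued hospitalization. The planned Fisher comparison does not allow for either.

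The documents do not let the bias be bounded. Under the day-28 versus day-100 assumption, false rejection runs from 0.03 to 0.06 when 90% of events fall by day 28. It is 0.06 to 0.42 when 60% do, and 0.47 to nearly 1 under a constant hazard with day-28 incidence of 5% to 30%. If controls are in practice questioned at monthly calls over a comparable period, the bias would be much smaller. Event timing, background rate, actual control follow-up and the share of patients with two or three doses are all assumptions here.

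**What to change.** 1. In both arms, collect adverse and serious adverse events from randomization to one fixed study day that covers the longest treated window with dosing tolerances. That is slightly beyond day 129: day 131, or day 133 if the tolerances accumulate. At minimum, run the between-arm comparison over a common fixed window, such as randomization to day 29.
2. Reword the adverse-event definition in Section 8.2 to refer to a participant enrolled in the study.
3. Include randomized controls in the safety population (Sections 13.5.2 and 13.6).
4. Restrict Fisher's test in Section 13.6, and the matching tests in Section 13.2, to events within the common window.
5. Reconcile the call schedules in Sections 7.7, 10 (note f), 10.3 and 13.1, so that one contact covers the end of the window in both arms.

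Manufacturer reporting in Section 8.4.4 can stay tied to dosing.

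The cost is protocol wording plus a few more weeks of adverse-event questions at phone contacts already planned. For a patient with one dose and a day-131 end, that is 131 − 101 = 30 extra days. The day-29 alternative uses contacts already scheduled, but gives no comparison of later events.
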